## **G.2 Monitoring procedures**

Monitoring visits will be conducted during and at the closure of the clinical study in accordance with Medtronic SOPs and the Monitoring Plan.

It is the responsibility of Medtronic to ensure proper monitoring of the study. Appropriately trained Medtronic personnel or delegates appointed by Medtronic will perform study monitoring at the study center in order to ensure that the study is conducted in accordance with the Clinical Investigation Plan, the signed Clinical Trial Agreement (CTA), and applicable regulatory requirements. Medtronic must therefore be allowed access to the subjects' clinic and hospital records when requested as per the Patient Informed Consent and CTA.

### *G.2.1 Accessibility of investigation site staff and study materials*

The principal investigator(s), his/her delegate(s) and the study coordinator(s) shall be available to Medtronic field personnel and the Clinical Study Manager. This accessibility is of particular importance for reviewing data in the Case Report Form. Direct access to patient medical files for source data verification will need to be granted and prepared prior to any monitoring visits.

### *G.2.2 Audits and investigation site inspections*

In addition to the foreseen monitoring visit, Medtronic may conduct audits at participating investigation sites. The purpose of an audit is to verify the adequate performance of the clinical study related activities. Independent of the employees involved in the clinical study. Regulatory authorities may also perform inspections at participating investigation sites. Any regulatory authority inspection announcements shall be forwarded immediately to the Medtronic study contact person.

The investigator and/or institution shall permit Medtronic and regulatory bodies direct access to source data and documents, taking into account any restrictions due to local law, to perform clinical study-related monitoring, audits, EC review and regulatory inspections.

## **G.3 Study suspension or early termination**

### *G.3.1 Early study suspension or termination*

Medtronic or Regulatory Authority may decide to suspend or prematurely terminate the clinical study. If the clinical study is terminated prematurely or suspended, Medtronic shall promptly inform the Principal Investigator of the termination or suspension and the reason(s) for this. The investigator shall then promptly inform the reviewing EC, the study subject and their General Practitioner.

### *G.3.2 Early investigation site suspension or termination*

Medtronic or EC may decide to suspend or prematurely terminate an investigation site (e.g. in case of expiring approval of the reviewing EC, non-compliance to the Clinical Investigation Plan or lack of enrollment). If an investigation site is suspended or prematurely terminated, Medtronic shall promptly inform the investigator of the termination or suspension and the reason(s) for this. The investigator shall then promptly inform the reviewing EC, the study subject and their General Practitioner. When the risks are found to outweigh the potential benefits or when there is conclusive proof of definite outcomes, investigators must assess whether to continue, modify or immediately stop the clinical study in the respective investigation site and immediately inform the sponsor and EC if applicable.

## **G.4 Study close out**

Study close out occurs when Medtronic and/or regulatory requirements have been satisfied per the Clinical Investigation Plan and/or by a decision by Medtronic, whichever occurs first. Medtronic will inform the Principal Investigator when this occurs. Study closure also includes, but is not limited to data query resolution. The study closure process is complete upon distribution of the Final Report or after final payments, whichever occurs last.

# **H DATA ANALYSIS AND REPORTING**

## **H.1 Analysis of clinical data**

Descriptive statistics will be used to summarize the patient demographic and clinical characteristics at baseline. Data for qualitative variables will be presented as prevalence rates (total number of subjects, number of events, and percent). Data for continuous variables will be summarized using measures of central tendency and dispersion.

All subjects who signed the informed consent document will be defined as the All Enrolled Population. The Analysis Population is defined as subjects who are enrolled and complete at least one of the walking exercises. Subjects who are enrolled but are found to have a protocol deviation such that the clinical interpretability of the results obtained from the patient is impacted, will not be included in the primary analysis, but will be reported in the patient disposition table. The analysis exclusion of subjects due to inclusion or exclusion criteria violation or a significant CIP deviation will be decided upon by the study team blinded without prior knowledge of statistical analysis results. Safety will be reported on the All Enrolled Population and the primary objective will be reported on the Analysis Population.

During the study all movement data is continuously collected. The primary endpoint for this study are the gait parameters obtained from the Reveal LINQ – REEF Research System, Rev 1.0 (accelerometer) and the external reference system (i.e. validation accelerometer and/or computer assisted rehabilitation system). All data processing will be performed offline.

The gait speed (and additional parameters) will be calculated from the Reveal LINQ accelerometer signals, from the validation accelerometer and/or from the computer assisted rehabilitation system. Correlation coefficients between the Reveal LINQ parameters and those from the reference system will be calculated for each maneuver (4MGS, FTSTS, ETGUG and 6MHW). The agreement between the Reveal LINQ derived parameters and the reference parameters will be reported and visualized using Bland and Altman plots.

The agreement between the parameters derived during the different maneuvers will also be evaluated using correlation coefficients and Bland-Altman plots.

Any change to the data analysis methods described in the Clinical Investigation Plan, and the justification for making the change, will be described in the clinical study report. Additional exploratory analyses of the data will be conducted as deemed appropriate.

Missing data will not be imputed. The number included in each analysis will be reported so that the reader can assess the potential impact of missing data.

## H.2 Publication Policy

Publications and presentations referring to this clinical study will be coordinated by Medtronic to allow the use of all available data. The following publication policy will have to be adhered to by the participating investigation site:

Medtronic may intend to publish the results of the study in scientific journals and congresses.

Authorship on any publication(s) resulting from this clinical study will be assigned according to the latest ICMJE Recommendations (“Recommendations for the Conduct, Reporting, Editing, and Publication of Scholarly Work in Medical Journals”, 2013).

The number of authors will be dependent on the regulations of the concerning journal.

There are no plans to form a publication committee. Publication activities will be assessed after the study is completed and any collaboration with the investigator will be determined at that time.

Based on the principle that Medtronic owns the data of this clinical study, the investigation site may access and use the data provided by itself for scientific publications following prior approval by Medtronic.

Medtronic as the owner of the data can use the data and/or any results derived from the data or publications based on that data for marketing purposes, further research and development of devices or educational use.

The study sponsor will collect data in such way that no subject can be identified, and monitor study records.

Participating subjects will not be identified by name in any published reports about the clinical study.

## I.2 Advisory committees

This feasibility study will not involve any Data Monitoring Committee, Steering Committee, Safety Committee or Adverse Event Advisory Committee as no clinical/therapeutic intervention is being applied or evaluated, the participants will be invited to wear external monitoring equipment during the study visit. Additionally, the study will be conducted at one center only which has experience and operating procedures related to the use of this monitoring equipment.

### *I.2.1 Data Monitoring Committee*

No Data Monitoring Committee will be installed for this clinical study as no interventions intended to prolong life or reduce risk of a major adverse health outcome (e.g., cardiovascular events) are evaluated, for which favorable or unfavorable study results suggest study

termination. Nor there are safety concerns suggesting the need for a Data Monitoring Committee.

*1.2.2 Publication Committee*

There are no plans to form a publication committee

**1.3 Records and reports**

*1.3.1 Investigator records*

At a minimum, the following records must be kept by the investigator:

- Clinical Investigation Plan and, any amendments
- EC notification, correspondence and approval
- EC voting list
- Medtronic and EC approved Patient Informed Consent
- Fully signed clinical investigation agreement and confidentiality agreement (if not included in the clinical investigation agreement)
- Insurance certificates
- Completed Delegated Task List and Curriculum Vitae of all investigation site personnel
- Training documentation of all investigation site personnel
- Relevant communications that pertains to the clinical study
- Subject identification log
- Signed, dated and fully executed informed consent forms
- Fully executed CRFs and corrections
- Device accountability records
- Final report

All study related information and records are subject to inspection and must be retained for a period of two years after study termination or closure or longer if required by local or hospital regulations

*1.3.2 Investigator reporting responsibilities*

The investigator is responsible for the preparation (review and signature) and submission to Medtronic of all case report forms and deviations from the clinical investigation plan. If any action is taken by the EC with respect to the study, the information must be forwarded to Medtronic immediately. Reports are subject to inspection and to the retention requirements as described above for investigator records. The investigator shall prepare and submit in a complete, accurate and timely manner the reports listed in Table 4.

Table 4: Investigator Reports		
Reports	Submit To	Description / Constraints
Withdrawal of EC approval	Medtronic	Notification immediately after the investigator first learns of withdrawal of EC approval.

Table 4: Investigator Reports		
Reports	Submit To	Description / Constraints
Study Deviations	Medtronic, EC, as applicable	Any deviation from the CIP shall be recorded together with an explanation for the deviation. Deviations shall be reported to the sponsor who is responsible for analyzing them and assessing their significance.  Note: When relevant, Ethics Boards, competent authorities or the appropriate regulatory bodies should be informed.
Failure to obtain informed consent	Medtronic, EC	Notification within five working days.
Progress Reports and final report (if required)	Medtronic, EC	Provide if required by local law or Ethics Board

### 1.3.3 Sponsor records

At a minimum, the sponsor will keep the following records:

- All essential study documents and correspondence that pertains to the clinical study
- CIP and any amendments
- Curriculum vitae of investigators and site staff
- Delegated Task Lists and training records of investigators and site staff
- EC approvals/notifications/voting list
- Signed Clinical Investigation Agreements
- Insurance certificates
- A copy of Device accountability records
- Shipping records for study devices/equipment
- Medtronic and EC approved Patient Informed Consents
- monitoring visit reports
- Study training records for site personnel and Medtronic personnel involved in the study.
- Final report of the study.
- Fully executed CRFs and corrections

Medtronic records and reports will be stored in locked file cabinets at Medtronic during the course of the study. After closure of the study, all records and reports will be archived indefinitely.

### *1.3.4 Sponsor reporting responsibilities*

Medtronic shall prepare and submit the complete, accurate, and timely reports listed in Table 5. In addition, Medtronic shall, upon request of reviewing EC or regulatory agency, provide accurate, complete and current information about any aspect of the study.

Table 5: Sponsor Reports		
Report	Submit to	Description
Early termination or suspension of the clinical study	Investigator	Provide prompt notification of termination or suspension and reason(s)
	EC	Inform the EC promptly, if required per local law
Withdrawal of EC approval	Investigator	Notify all applicable investigators, if required by local laws or EC
Progress Reports	EC	Submit to EC, if required per local law
Final Report	EC	Submit to EC, if required per local law
Study Deviation	Investigator	Site specific study deviations will be submitted to the investigator quarterly.

### *1.3.5 Record retention*

The investigator must retain the Investigator Site File, patient medical files and CRFs in accordance with local law and regulations.

The investigator should take measures to prevent accidental or early destruction of the clinical study related materials.

## **I.4 Miscellaneous**

### *1.4.1 Insurance*

The Bakken Research Center B.V is a wholly owned subsidiary of Medtronic Inc., which as the parent company of such entity maintains appropriate clinical study liability insurance coverage as required under applicable laws and regulations and will comply with applicable law and custom concerning specific insurance coverage. If required, a Clinical Trial Insurance statement/certificate will be provided to the EC.

### *1.4.2 Subject compensation and indemnification*

The subjects enrolled will not receive any compensation for the participation in the study. They will only receive compensation for reasonable, necessary and properly documented (e.g., copy of train ticket) travel expenses (for example, kilometer compensation, public transportation or parking costs) in connection with participation in the study.

### *1.4.3 Subject confidentiality*

The study sponsor will collect data in such way that no subject can be identified, and monitor study records. All records and other information about subjects participating in this study will be treated as confidential.

Participating subjects will not be identified by name in any published reports about the study.

## J RISKS AND BENEFITS

### J.1 Anticipated Clinical Benefits

The objective of this study is to collect data from the subjects with no direct clinical benefit to them. However, this study design will be the first to evaluate the feasibility of using the Reveal LINQ™ to monitoring walking patterns, which could be useful for the identification of frailty in its early stage, which is important because interventions may potentially prevent, or delay the clinical consequences of frailty, therefore the benefit may be for future patients.

### J.2 Risks

Since the study devices will not be used for therapeutic purposes, but just to collect accelerometer data and considering the nature and duration of the study, no major risks to the subjects are expected with this study. It may be possible to anticipate local events at the level of the study tool/product placement (i.e. Allergic reaction, Skin irritation) - which the medical grade adhesive placed below the device should prevent - and/or events related to the physical execution (i.e. accidental fall) of the walking exercises.

Any further detail coming from risk assessment on potential risks and risks minimization will be provided under a separate cover.

### L.2 Case Report Forms

Case Report Form will be provided it under a separate cover.

### L.3 Abbreviations

ADE	Adverse Device Effect
AE	Adverse event
AEAC	Adverse Event Advisory Committee
CA	Competent Authority
CAREN	Computer Assisted Rehabilitation Environment
CV	Curriculum Vitae
DTL	Delegated Task List
CIP	Clinical Investigation Plan
CRF	Case Report Form
DMC	Data Monitoring Committee
EC	Ethics Committee
CRF	Case Report Form
ETGUG	Expanded Timed Get-Up-and-Go
FTSTS	Five Times Sit to Stand
6MW	Six Minute Walk
4MGS	Four Meter Gait Speed

FU	Follow up
HD	Hard Drive
HF	Heart Failure
HRV	Heart rate variability
NHYA	New York Heart Association
PIC	Patient Informed Consent
SD	Secure Digital
SOP	Standard operating procedure

Medtronic Statistical Analysis Plan

Clinical Investigation Plan Title	Frailty Walking Patterns (FRAP) Study
Clinical Investigation Plan Version	Version 1, 17 FEB 2016
Sponsor/Local Sponsor	Medtronic, Bakken Research Center B.V. [name] The Netherlands
Document Version	V. 1.0 20 APR 2017
Confidentiality Statement 
The information contained in this document is confidential and the proprietary property of Medtronic. Any distribution, copying, or disclosure without the prior written authorization of Medtronic is strictly prohibited. Persons to whom the information is disclosed must know that it is confidential and that it may not be further disclosed by them.
	

Table of Contents

1. Version History	3
2. List of Abbreviations and Definitions of Terms	3
3. Introduction.....	3
4. Study Objectives	3
5. Investigation Plan.....	4
6. Determination of Sample Size	4
7. Statistical Methods	5
7.1. Study Subjects.....	5
7.2. General Methodology.....	6
7.3. Center Pooling.....	6
7.4. Handling of Missing, Unused, and Spurious Data and Dropouts.....	7
7.5. Adjustments for Multiple Comparisons.....	7
7.6. Demographic and Other Baseline Characteristics	7
7.7. Treatment Characteristics.....	7
7.8. Interim Analyses.....	7
7.9. Evaluation of Objectives	7
7.10. Safety Evaluation.....	8
7.11. Health Outcomes Analyses	8
7.12. Changes to Planned Analysis.....	8
8. Validation Requirements	8
9. References	8

1. Version History

Version	Summary of Changes	Author(s)/Title
1.0	Not Applicable, New Document	[name], Therapy SME/Biostatistician

2. List of Abbreviations and Definitions of Terms

Abbreviations should be indicated in parentheses at first appearance in the text. Abbreviations should appear in alphabetical order.

Abbreviation	Definition
4MGS	4 Meter Gait Speed
FTSTS	Five Times Sit to Stand
ETGUG	Expanded Timed Get-Up-and-Go
6MHW	Six Minute Walk (6MW) Test

3. Introduction

The FRAP Study is a prospective, non-randomized, single-center, post-market interventional study.

The aim of this study is to evaluate sit-stand phases and gait speed detection using an externally worn LINQ compared to an external reference (3D accelerometer, and/or the CAREN system) in one center in the Netherlands.

The intended use of the Reveal LINQ in this study is not for medical purposes, but exclusively for technical reasons, therefore the Reveal LINQ is considered a non-medical device in this study. The Reveal LINQ device is used externally with the investigational software RAMware REEF Research System, Rev 1.0 onboard. The software is downloaded through the 2090 programmer. Since RAMware REEF Research System is an accessory to the Reveal LINQ it is also classified as a non-medical device.

Subjects perform part (i.e. Six Minute Walk Test, 4 Meter Gait Speed Test) of the walking exercises inside the Computer Assisted Rehabilitation Environment (CAREN) system, to record additional subject position information.

The Clinical Investigation Plan V. 1 17 FEB 2017 has been used to develop this Statistical Analysis Plan with the purpose to describe the Final Analysis foreseen for FRAP Study.

4. Study Objectives

The primary objective of this study is to compare Gait parameters (i.e. gait speed, walking patterns) derived from the Reveal LINQ accelerometer signals during Six Minute Walk (6MW) Test, 4 Meter Gait Speed (4MGS) Test, Five Times Sit to Stand (FTSTS) Test, Expanded Timed Get-Up-and-Go (ETGUG) Test with those obtained from a validation accelerometer and the CAREN system.

5. Investigation Plan

This is a prospective, non-randomized, single-center post-market interventional study. The Study will take place in the Netherlands at one investigation site. No randomization and no blinding will be used in this Study.

Inclusion criteria

- Chronic Heart Failure in NHYA class II and class III.
- Willing to sign the informed consent form.
- At least 18 years of age.

Exclusion criteria

- Not able to walk continuously for a period of 6 minutes and perform the walking exercises as necessary for the study protocol.
- Any known allergy to Titanium
- Any concomitant conditions which in the opinion of the investigator would not allow accurate measurement of gait and frailty parameters with an externally worn device.
- Any concomitant condition which in the opinion of the investigator would not allow a safe participation in the study.
- Enrolled in another study that could confound the results of this study, without documented pre-approval from a Medtronic study manager

6. Determination of Sample Size

The FRAP study is primarily designed to evaluate the possibility of extracting walking patterns from the accelerometer embedded in the Reveal LINQ.

A sample size of approximately 20 subjects will be enrolled to see if reproducible results indicating feasibility of extracting walking patterns could be obtained. No formal statistical hypotheses are being tested.

7. Statistical Methods

7.1. Study Subjects

7.1.1. Disposition of Subjects

Disposition of patient will be reported following the STROBE Statement Checklist (2). Number of individuals at each stage of study (number of total assessed for eligibility, number enrolled, number analyzed) will be reported (see the flowchart example). Reason for not participation at each stage will be reported where known.

Table. Number of Subject Enrollments by Site

Site	Date of First Enrollment	Eligible patient	Subjects Enrolled (N = X)	Subjects Analyzed (N = X)
Xxxxx	XXDDDDYYYY	N	X (Y%)	X (Y%)

7.1.2. Clinical Investigation Plan (CIP) Deviations

Reasons for deviation are:

- Patient informed consent procedure
- Patient eligibility criteria
- Study data collection and reporting

The following tables will describe study deviations:

Table. Types of Study Deviations by reason

Study Deviation Type	Number of Deviations (Number,% of Subjects)		
	Subjects in (N = N1)	Subjects in (N = N2)	Total Subjects (N = N)
Reason#1	NE (NS, Y%)	NE (NS, Y%)	NE (NS, Y%)
Reason#1	NE (NS, Y%)	NE (NS, Y%)	NE (NS, Y%)
....
Total	NE (NS, Y%)	NE (NS, Y%)	NE (NS, Y%)

Listing. Reason for exclusion

Reason for exclusion	Reason for excluding from analysis
Patid#1	Text
Patid#2	
....	
Patid#N	

7.1.3. Analysis Sets

All subjects who signed the informed consent document will be defined as the Full Analysis Set (FAS). Subjects who are enrolled but are found to have a protocol deviation such that the clinical interpretability of the results obtained from the patient is impacted, will not be included in the primary analysis, but will be reported in the patient disposition table.

The Analysis Population is defined as subjects that are enrolled in the study, who signed Informed Consent Form (ICF), fulfilled the inclusion and exclusion criteria and with a good quality of Holter, LINQ, Actigraph and CAREN data recordings and who completed at least one of the walking exercises. The analysis exclusion of subjects due to inclusion or exclusion criteria violation or a significant CIP deviation will be decided upon by the study team blinded without prior knowledge of statistical analysis results.

Population set	Baseline assessment	Primary and Secondary Endpoints
FAS		
Analysis Population	√	√

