7.2. General Methodology

Descriptive statistics will be used to summarize the patient demographic and clinical characteristics at baseline. Data for qualitative variables will be presented as prevalence rates (total number of subjects, number of events, and percent). Data for continuous variables will be summarized using measures of central tendency and dispersion.

During the study all movement data is continuously collected. The primary endpoint for this study are the gait parameters obtained from the Reveal LINQ – REEF Research System, Rev 1.0 (accelerometer) and the

external reference system (i.e. validation accelerometer and/or computer assisted rehabilitation system). All data processing will be performed offline.

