7.4. Handling of Missing, Unused, and Spurious Data and Dropouts

Missing data will not be imputed. The number included in each analysis will be reported so that the reader can assess the potential impact of missing data.

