7.12. Changes to Planned Analysis

No major modifications are required from the analyses planned in the protocol.

8. Validation Requirements

To ensure the quality of the results provided for the study in the form of tables, listings and figures the following processes are used:

- Statistical analysis will be done by qualified MDT personnel following best practices.
- Statistical results will be reviewed and confirmed by a second MDT statistician or designee.

According to Medtronic SOPs the validation will be implemented for statistical outputs

9. References

1. <http://www.strobe-statement.org/index.php?id=available-checklist>

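### SAP 7.1.3 adds an undefined, undeclared recording-quality condition on four systems to the protocol's Analysis Population; it may select on LINQ performance and, read literally, discards valid LINQ-Actigraph pairs

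*SAP*

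**What the plan says.** Protocol H.1: "The Analysis Population is defined as subjects who are enrolled and complete at least one of the walking exercises". The same section excludes subjects with a deviation that impairs clinical interpretability. The study team makes exclusions for eligibility violations or significant deviations without knowing the results. H.1 adds that "the primary objective will be reported on the Analysis Population".

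SAP 7.1.3 uses the same name for a narrower set: eligible, consented subjects "with a good quality of Holter, LINQ, Actigraph and CAREN data recordings and who completed at least one of the walking exercises". Neither document defines good quality, names an assessor, or says whether it is judged by subject, by test or by signal. The SAP's table of analysis sets ticks baseline and endpoints for the Analysis Population and nothing for the FAS.

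SAP 7.12 states: "No major modifications are required from the analyses planned in the protocol".

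Other provisions that bear on the point:
- SAP 7.2 describes the reference as "validation accelerometer and/or computer assisted rehabilitation system".
- SAP 7.4: "The number included in each analysis will be reported so that the reader can assess the potential impact of missing data". Its heading covers spurious data, but the text gives no rule for them.
- SAP 7.1.2 lists "Study data collection and reporting" among the reasons for deviation.
- The protocol synopsis and SAP section 3 place only the six-minute walk (6MW) and the 4-metre gait speed test (4MGS) in CAREN.

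**The concern.** Protocol C.3 says that the study is about whether walking patterns can be extracted from the LINQ accelerometer. With no hypothesis test, the description of agreement is the main output, so it matters who enters it.

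**Selection on the device under study.** If good quality means only that a parameter can be derived, the LINQ part of the condition changes little, because a signal that gives no value drops out of a paired analysis anyway. If it is stricter, signals that are poor but analysable are removed, and LINQ agreement may look better than it is.

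**Loss of valid pairs.** The four systems are joined by a plain conjunction at subject level. Read literally, one failed system removes the subject from everything, including the sit-to-stand (FTSTS) and get-up-and-go (ETGUG) comparisons that do not use CAREN. A poor Holter ECG would do the same, although heart rate variability is the only endpoint in protocol C.2 that plainly needs an ECG.

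**No full safeguard.** A bad recording that counts as a data-collection deviation may fall under the blinded decision. A poor signal that is not a deviation, such as one from a hardware fault, does not.

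**Working it through.** **The plan's own figure.** The planned size is approximately 20. It is not derived from precision or power, which is acceptable for a feasibility study, so there is nothing to reproduce.

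**The two definitions side by side**

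| Element | Protocol H.1 | SAP 7.1.3 |
|---|---|---|
| Enrolled, at least one exercise done | yes | yes |
| Eligibility | violations can be excluded, decided blind | must be fulfilled; same blinded decision |
| Good Holter, LINQ, Actigraph and CAREN recordings | absent | required, no criterion |

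The eligibility wording is close to equivalent. The recording condition is new.

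The literal reading also conflicts with the rest of the SAP. A subject who completes only FTSTS or ETGUG satisfies the one-exercise rule but has no CAREN test recording. Requiring both references does not fit the and/or definition in 7.2, and exclusion of whole subjects does not fit counting the number in each analysis in 7.4.

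**Illustration 1: selection on LINQ quality.** The assumptions, none from the documents, are 20 subjects with one difference each and equal mean differences, of whom m have k times the SD of the others. Relative to the retained subjects, the full-set SD is sqrt(((20 − m) + m·k²)/20). Excluding the m subjects narrows the limits of agreement by 1 − 1/(that ratio).

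Example, m = 2 and k = 2: sqrt((18 + 8)/20) = 1.140, and 1 − 1/1.140 = 12.3%.

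| k | m = 1 | m = 2 |
|---|---|---|
| 1 | 0% | 0% |
| 1.5 | 3.0% | 5.7% |
| 2 | 6.7% | 12.3% |
| 3 | 15.5% | 25.5% |

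**Illustration 2: pairs lost under the literal rule.** Assume that each recording is good with probability q, independently. Holter and LINQ count as one recording, because the Holter stores the LINQ accelerometer signal (protocol B.2). A usable LINQ-Actigraph pair for FTSTS or ETGUG then needs two recordings (20·q²). The literal rule also needs CAREN (20·q³). The half-width of a 95% CI for a limit of agreement, in SDs of the differences, is t(0.975, n − 1)·sqrt(1/n + 1.96²/(2(n − 1))).

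| q | Pairs available, 20q² | Pairs kept, 20q³ | Lost | Half-width, available | Half-width, kept | Ratio |
|---|---|---|---|---|---|---|
| 0.95 | 18.05 | 17.15 | 0.90 | 0.865 | 0.892 | 1.031 |
| 0.90 | 16.20 | 14.58 | 1.62 | 0.923 | 0.986 | 1.068 |
| 0.85 | 14.45 | 12.28 | 2.17 | 0.991 | 1.101 | 1.110 |

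The interval would be about 3, 7 or 11% wider. SAP 7.9 does not plan such an interval, so this serves only as a measure of lost information.

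If Holter and LINQ instead fail independently, the literal rule keeps 20·0.90⁴ = 13.1 subjects at q = 0.90, against 16.2 with a usable LINQ-Actigraph pair.

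**The case against.** The strongest reply has four parts.

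**Disclosure.** Protocol H.1 sends "Any change to the data analysis methods described in the Clinical Investigation Plan" to the clinical study report, and SAP 7.12 denies only major modifications. No breach is shown. That is correct, and the change could still be explained in the report. The SAP itself nevertheless does not declare it.

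**Reading.** The passages that conflict with the literal reading can be taken as evidence that quality was meant to apply to the signals relevant to each comparison. No pair would then be lost to CAREN. This is plausible, but the text of 7.1.3 does not say it, and an analyst following that text would exclude whole subjects. The Holter route is weaker than the CAREN route, because Holter quality may simply mean an intact LINQ file.

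**Direction.** The condition also screens the reference systems, and a bad reference recording would make LINQ look worse than it is. Requiring valid reference data is ordinary practice in a method comparison. The net direction is therefore unknown. What remains objectionable is that LINQ quality is a condition of entry and has no stated criterion.

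**Visibility.** The disposition with reasons, the listing of exclusions and the number in each analysis would show who was dropped, and exploratory analyses allow an unfiltered result. All true, but none of them commits to that result or fixes the criterion in advance.

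**Conclusion.** The concern holds and should be fixed. Three elements rest on the text alone: the condition is added to the protocol's population, it is undefined, and SAP 7.12 does not declare it.

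The consequences are conditional. Selection in favour of LINQ arises only if good quality is stricter than derivability; otherwise that effect is nil. Loss of FTSTS and ETGUG pairs arises only under the literal subject-level reading.

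The documents give neither failure rates nor an SD of differences, so both sets of figures are illustrations. The selection effect could be material if a few subjects have much noisier LINQ signals. The pair loss is modest, and less if failures cluster in the same subjects. No hypothesis or acceptance margin is at stake; the effect is on how far the reported agreement can be trusted.

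**What to change.** - **SAP 7.1.3:** restore the protocol's Analysis Population and delete the four-system condition. Include a subject in each test and device-pair comparison for which both signals yield the parameter, with CAREN used only for 6MW and 4MGS.
- **SAP 7.4:** state any quality exclusion and its criterion, at signal and test level, and have it judged blind to the LINQ-reference difference. This also supplies the missing rule for spurious data.
- **Results:** for each test, report the number with usable LINQ data out of those who performed it.
- **SAP 7.12:** declare any remaining departure from the protocol.

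Optional additions are an exact 95% CI for the LINQ yield (for example, 18/20 = 90%, Clopper-Pearson 68 to 99%) and the good-quality subset as a sensitivity analysis.

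The cost is SAP wording and one count per test, with no new data. Reported agreement may look slightly less favourable, and poor reference recordings could count against LINQ unless the 7.4 rule removes them.
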